## 6.3. Study Objectives

The primary study objective is to determine if the hemostatic efficacy of MIR-treated plasma stored Trima Accel® Aph PLTs (MIRASOL) is non-inferior to Conventional plasma stored Aph PLTs (CONTROL) in subjects with hypoproliferative thrombocytopenia requiring PLT transfusions.

The secondary study objectives include comparing other efficacy and safety endpoints between the MIRASOL and CONTROL groups.

Unless otherwise specified, comparisons of each endpoint will be presented as (MIRASOL vs CONTROL). The primary analyses will be based on the observed data in the mITT set. The secondary and exploratory endpoints are summarized below. An in-depth discussion of the analysis of these

endpoints is provided in Sections 8.1 to 8.3, respectively. The safety endpoints are also summarized below and are discussed in detail in Section 8.4

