## 7.14. On- Off-Protocol Transfusions

On- and Off-Protocol Transfusion definitions are as follows:

Off-Protocol Transfusion: any kind of PLT transfusion, other than those to which the subject was randomized (MIR PLTs or REF PLTs), regardless of the reason for the transfusion. For subjects

randomized to MIR treatment (MIRASOL), ISBT codes defined by the sponsor as 'Control Allowed' or 'Control NOT Allowed' meet this criterion. For subjects randomized to CONTROL, ISBT codes defined by the sponsor as 'MIRASOL' or 'MIRASOL Not Used' meet this criterion.

On-Protocol Transfusion: non-MIR or MIR treated platelet product transfused according to randomization assignment. For subjects randomized to MIR treatment (MIRASOL), ISBT codes defined by the sponsor as 'MIRASOL' or 'MIRASOL Not Used' meet this criterion. For subjects randomized to CONTROL, ISBT codes defined by the sponsor as 'Control Allowed' or 'Control NOT Allowed' meet this criterion.

On- and off-protocol platelet transfusions will be reported on the SS and summarized by treatment group and reason for transfusion, i.e. prophylactic, therapeutic (bleeding event), and other. The total number of platelet transfusions and the number of transfusions on- and off-protocol will be reported. The mean, median, minimum and maximum number of transfusions per subject will be reported. The number and percent of subjects with at least 1 on-protocol transfusion will be reported along with the median, minimum, and maximum duration of the transfusion period in days. The number and percent of subjects who had at least 75% of transfusions on-protocol (part of the PPS definition) will also be reported.

Each subject's transfusion will be listed along with on- or off-protocol and non-compliance status described in Section 7.12.

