### 8.1. Primary Endpoint

Bleeding assessments based on the WHO Grading Scale for Bleeding will be conducted at baseline to assess eligibility prior to randomization, as well as daily starting on Day 0 and continuing to the post-transfusion bleeding assessment OR until transfusion independence (the last day of ten [10] consecutive days without a PLT transfusion). Each bleeding assessment will document the WHO Bleeding Scale components observed over the course of the prior calendar day, from 00:00 to 23:59. As such, the analysis of the Primary Endpoint, and Secondary Endpoint #2, will be based on bleeding assessments collected on Day 1 thru Day 28 which represent bleeds which occurred on Days 0-27.

The total number of days with WHO grade 2 or higher bleeding is obtained by counting the total number of calendar days (00:00 to 23:59) on which bleeding was assessed and found to be present. For example, if a subject has WHO grade 2 bleeding on Day 1, grade 2 bleeding on Day 2, and grade 3 bleeding on Day 3, this is considered 3 days of grade 2 or higher bleeding. Hematomas (bruises), petechiae, and purpura

[figure not shown]
(e.g., types of bleeding that occur under the skin) represent unique cases in which they are only counted as additional days of bleeding if they are new or manifest in another anatomical location.

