The timeline diagram provided below demonstrates the definition of an off-protocol window, which we sometimes refer to as an off-protocol interval of time. Consider an individual who was recruited and received on-protocol transfusions as needed from day 0 to day  $n-1$ . On Day  $n$  they received an off-protocol transfusion and on Day  $m$  they received their first subsequent on-protocol transfusion; no off-protocol transfusions were received beyond Day  $m$ . In order to avoid attributing bleeding outcomes to the randomized treatment arm when an off-protocol product is delivered we partition the full treatment period as follows. We define the intervals from day 0 to  $n-1$  and  $m$  to Day 27 as *on-protocol intervals*, and days  $n$  to  $m-1$  as an *off-protocol interval*. In the figure below bleeds are represented by red lines on Days 1-2 and on Day 26 for illustration.

To mitigate against the effect of the off-protocol transfusions in the primary endpoint analysis, bleeding data will be simulated for the off-protocol windows (e.g. intervals such as  $[n, m-1]$  above) using an

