individual-specific bleeding rate estimated as follows. If individual  $i$  has any off-protocol intervals of time, then an individual-specific bleeding rate will be computed as  $r_i^{on} = B_i^{on} / N_i^{on}$  where  $B_i^{on}$  is the number of on-protocol days during which this individual experienced, and had documented, at least WHO grade 2 or higher bleeding.  $N_i^{on}$  is the number of days on which bleeding was assessed during the on-protocol intervals for this subject. Then a) the number of days bleeding was assessed during the off-protocol interval will be computed ( $N_i^{off}$ ) and b) the number of these days during which WHO  $\geq 2$  grade bleeding is present will be simulated ( $B_i^{off}$ ) based on a right-truncated Poisson distribution using the individualized bleeding rate ( $r_i^{on}$ ). The right-truncation limit will be the total number of off-protocol days ( $N_i^{off}$ ) since there cannot be more bleedings days than there are days at risk. Specifically, for each individual, counts will be simulated from a Poisson distribution using  $r_i^{on} \times N_i^{off}$  as the mean. A simple rejection sampling technique [1] will be used to sample from the right-truncation distribution whereby all values generated which exceed the right truncation limit will be ignored until one is generated that satisfies the right truncation condition. This value will be labelled  $B_i^{off}$ . Then the total  $B_i^{on} + B_i^{off}$  will be taken as the number of bleeds for that individual experienced over  $N_i^{on} + N_i^{off}$  days of assessments; then  $\ln(N_i^{on} + N_i^{off})$  will be used as the offset.

If the bleeding rate estimated based on available data  $r_i^{on} = 0$  then there will be no bleeding days simulated for the off-protocol days ( $B_i^{off} = 0$ ) and the offset will still be calculated as  $\ln(N_i^{on} + N_i^{off})$ . Note that for individuals whose last transfusion is off-protocol, at most 10 days of bleeding data after the last transfusion will be simulated as patients going ten (10) days without a transfusion will have acquired transfusion independence.

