On occasions where a subject receives a mix of off-protocol and on-protocol units on the same day, they will be considered in an on-protocol period on that day. Transfusions can last more than one calendar day. The daily on- and off-protocol statuses will be assigned for the day the transfusion(s) starts. For subjects whose last transfusion is off-protocol, bleeding will be simulated until the subject completes the transfusion period or reaches transfusion independence. If the subject achieves transfusion independence prior to completing the transfusion period, the rules for transfusion independence will take over and subjects will be assumed to have zero bleeds and full follow-up from the day of transfusion independence until Day 27 inclusive (i.e. the remainder of the transfusion period).

Unless otherwise stated any subsequent analysis herein referring to the primary endpoint method will include the individualized simulated bleeding data for the off-protocol periods of time. This simulation will be done twice. Once at the IA and once at the final analysis. The set of simulations done for the primary efficacy analysis will be used for all subsequent analyses wherein off-protocol intervals are called to use simulated bleeding data.

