### 8.1.2. Secondary Analyses

#### First Secondary Analysis: Off-Protocol Intervals Included with No Adjustments

In a secondary analysis of the primary outcome all available bleeding assessment data, whether collected on- or off-protocol, will be used and attributed to the randomized treatment in the spirit of an intention to treat analysis. No imputation will be carried out for bleeding status on days following drop-out as the offset deals with censoring and the resulting variation in the days at risk.

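### The primary analysis discards observed bleeding on the day of an off-protocol transfusion and substitutes one unseeded random draw, which can bias the ratio toward non-inferiority

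*SAP*

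**What the plan says.** The references are to the SAP; the document filed as the protocol carries the same text.

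- Section 6.3: "The primary analyses will be based on the observed data in the mITT set".
- Section 8.1: each assessment records bleeding "observed over the course of the prior calendar day, from 00:00 to 23:59".
- Section 7.14: a transfusion is off-protocol if it is any platelet product "other than those to which the subject was randomized (MIR PLTs or REF PLTs), regardless of the reason for the transfusion". The section also summarizes off-protocol transfusions by reason, and therapeutic use for bleeding is one of the reasons.
- Section 8.1.1: the off-protocol interval runs from Day n, the day of the off-protocol transfusion, to Day m-1, the day before the next on-protocol one. "The daily on- and off-protocol statuses will be assigned for the day the transfusion(s) starts". A day with both on- and off-protocol units counts as on-protocol.
- Section 8.1.1: "bleeding data will be simulated for the off-protocol windows". The replacement is one Poisson value with mean r_on x N_off, truncated at N_off. Here r_on is the subject's own bleeding rate over on-protocol days and N_off is the number of assessed off-protocol days. If r_on is zero, "then there will be no bleeding days simulated for the off-protocol days".
- Section 8.1.1: "This simulation will be done twice. Once at the IA and once at the final analysis". No seed is stated, and no pooling over draws is planned for the primary analysis.
- Section 8.1.2, first secondary analysis: all observed bleeding is used and "attributed to the randomized treatment in the spirit of an intention to treat analysis".

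**The concern.** The stated aim of the rule is to avoid charging the randomized arm with bleeding that occurs while another product is being given. Starting the interval at the beginning of Day n goes further. It also removes a bleed earlier that day which led to the off-protocol unit and which arose under the randomized product. That day also drops out of r_on, so the replacement is drawn from a rate that ignores the triggering bleed.

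The rule is the same in both arms, so it distorts the ratio only if same-day, bleed-triggered switches are more frequent in one arm. More switching in MIRASOL is plausible. Under 7.12 and 7.14, a Control Allowed unit given to a MIRASOL subject is off-protocol but compliant, while a Mirasol unit given to a CONTROL subject is off-protocol and also non-compliant. In that direction the estimated ratio falls and the comparison with ln(1.6) becomes too easy to pass.

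The single draw adds a smaller problem: a confirmatory verdict can depend on a seed that nobody has fixed.

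**Working it through.** **One subject, with no assumed rates.** There are 28 assessed days. The only bleed is grade 3 on Day 9, an off-protocol unit is given later that day, and the next on-protocol unit is on Day 12. The off-protocol interval is Days 9 to 11, so N_off = 3 and N_on = 28 - 3 = 25. B_on = 0, so r_on = 0/25 = 0 and the simulated count is 0. The subject enters as 0 of 28 bleeding days instead of 1 of 28.

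**Calibration.** From 6.3.3 and 8.1.3: 279 per arm, margin 1.6, assumed ratio 1.1, one-sided 0.025, about 85% power. The implied standard error is ln(1.6/1.1)/(1.96 + 1.036) = 0.375/2.996 = 0.125. The stated power cannot be reproduced independently, because the documents give neither the control rate nor the dispersion. Dispersion was therefore solved from 279 x 0.125^2 = 4.36 = (1 + 1/1.1)/mu_C + 2 phi:

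- mu_C = 1.5: phi = (4.36 - 1.27)/2 = 1.54
- mu_C = 2: phi = (4.36 - 0.95)/2 = 1.70
- mu_C = 3: phi = (4.36 - 0.64)/2 = 1.86

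**Trial level.** Days were simulated at a true ratio of 1.6, with a negative binomial fit and a Wald interval. Assumptions: 1-4-day windows, and switches on 2%, 5% or 10% of MIRASOL bleeding days with none in CONTROL. There were 6,000 trials per scenario (Monte Carlo error about 0.2 points at 2.5%). False non-inferiority at 2 / 5 / 10%:

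| Subject risk, control mean | SAP rule | Observed data | Day n kept as observed |
|---|---|---|---|
| Gamma, 1.5 days | 3.2 / 5.2 / 9.8% | 2.4 / 2.4 / 2.3% | 2.3 / 2.3 / 2.2% |
| Gamma, 3 days | 2.8 / 4.2 / 7.9% | 2.2 / 2.2 / 2.0% | 2.2 / 2.1 / 1.9% |
| Beta, 3 days | 1.5 / 2.1 / 3.7% | 1.2 / 1.1 / 1.0% | 1.2 / 1.0 / 1.0% |

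The shares of MIRASOL subjects who switch are 4-8%, 10-18% and 18-29%, and the analysed ratio falls by 1.4-1.6%, 3.4-4.0% and 6.4-8.0%. With 10% triggers in MIRASOL and 5% in CONTROL, false non-inferiority is 2.1-5.2% against 1.2-2.3% with observed data.

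Two separate simulations with control mean 2 and 3-day windows agree:

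- Triggers of 5%/1% and 10%/2.5% (MIRASOL/CONTROL) gave 4.3% and 7.3%, against 2.2% and 3.1% with observed data.
- MIRASOL-only triggers of 5% and 10% gave 5.7% and 10.2%, and 10% versus 5% gave 5.1%. Observed data gave 1.9-2.4% and the Day n fix 2.0-2.3%.

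At 20%/5%, 1-day and 3-day windows gave nearly the same result (17.3% and 17.7%), so the loss of Day n drives the bias.

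**When the bias is absent or reversed.**

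- Switching unrelated to bleeding: 2.5% against 2.4% with observed data.
- Equal triggering in both arms: 2.5% against 2.5%.
- More switching in CONTROL (5%/40%): the estimated ratio rises to 2.37 and false non-inferiority is 0%.
- A switch the day after an isolated bleed: ratio 1.60, 2.1%.
- A switch the day after, with bleeding that persists from day to day: 5.6% at 20%/5%.

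**Single draw.** The between-draw SD of the log ratio is 0.003-0.015, against a standard error of about 0.12-0.15. Two seeds give different verdicts in 0.1-2.7% of trials at ratio 1.6 and in 2.6-4.4% at a borderline ratio of 1.25. The model standard error was above, or within 2% of, the empirical SD in every run, so it is not understated.

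**Truncation.** The truncated mean falls below r_on x N_off by 28% at r = 1, N = 5, but by only 0.7% at r = 0.25, N = 5. The effect on the log ratio is at most 0.006.

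**The case against.** The strongest reply is that the bias is conditional. It needs switches that are prompted by bleeding, given on the same calendar day, purely off-protocol and more frequent in MIRASOL. The documents give no switching rate, arm split or reason, and the compliance rule in 7.12 supports more switching in MIRASOL but not switching because of bleeding. This stands: the direction is plausible and not established. At the low end the inflation is also small; under the beta model with 2% or 5% triggers, false non-inferiority stays below 2.5%.

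The second reply is that the rule is deliberate and the first secondary analysis in 8.1.2 would expose a problem. That is only partly a safeguard, because the non-inferiority decision is not tied to that analysis. The window-excluded analysis also drops Day n. The per-protocol, missing-data, Poisson and subgroup analyses and the interim futility model reuse the simulated data or its convention.

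Third, repeated draws from a fixed r_on are not full multiple imputation, and subjects with r_on = 0 receive zero every time. That is correct. The repetition is meant to remove seed dependence; it is not offered as a variance correction. Programming procedures outside these documents may control the seed, but the SAP does not state one.

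Finally, the conflict with 6.3 is a matter of wording. It is still a conflict, and the precedence rule in 7.4 covers only the general conventions of that section.

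**Conclusion.** The point holds and should be fixed. On the text alone, a bleed that precedes and prompts a purely off-protocol transfusion on the same day is removed from the primary analysis, the replacement can be exactly zero, and 6.3 describes the analysis differently. That the error favours non-inferiority depends on bleed-triggered switching being more common in MIRASOL, which the documents neither show nor exclude. With MIRASOL-only triggers on 5-10% of bleeding days, false non-inferiority at the margin is roughly 2-10%, against 1.0-2.4% with observed data. These sizes also depend on assumed control means and a dispersion calibrated to the stated power. The unfixed seed matters mainly for borderline results, and truncation is minor. Confidence in the size is medium.

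**What to change.** In 8.1.1:

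1. State that Day n keeps its observed bleeding assessment and counts as on-protocol, and that simulation covers Day n+1 to Day m-1 only.
2. Pre-state the seed, repeat the draw at least 50 times, fit the negative binomial model to each completed dataset, and pool with PROC MIANALYZE (already used in 8.1.2) for the comparison with ln(1.6). Say that this removes dependence on one draw while r_on stays fixed.
3. As a minor improvement, draw from Binomial(N_off, r_on), which needs no truncation.

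In 6.3, replace the reference to observed data with wording that matches 8.1.1.

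The cost is a few sentences and a loop in existing SAS code, plus carrying the same Day n rule and draws into the analyses that reuse them: the window definition in 8.1.2, the sensitivity, per-protocol and subgroup analyses, and the interim model. There are two downsides. Bleeding after the off-protocol unit on Day n is charged to the randomized arm. The triggering bleed also enters r_on, which overstates the MIRASOL ratio by under 0.5% with 1-4-day windows and by 1.4-2.7% with 10-day windows (false non-inferiority 1.3-1.9%). That error is conservative for non-inferiority. None of the runs reported here tests the fix when bleeding persists from day to day, so the observed-data analysis should be reported beside the primary result.

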### 8.1.1. Primary Analysis

The MIRASOL vs CONTROL group will be compared with respect to the number of days of WHO grade 2 or higher bleeding. This will be carried out by fitting a negative binomial regression model with an offset defined as the natural logarithm ( $\ln$ ) of the number of days that bleeding was assessed in order to account for the fact that subjects may have different numbers of bleeding assessment days. As an example, if a subject had bleeding assessed on only 10 of 28 days, an “offset” of  $\ln(10)$  bleeding assessment days is incorporated into the linear predictor of the model. Similarly, if bleeding is assessed on each of the full 28 days of the planned treatment period, an offset of  $\ln(28)$  bleeding assessment days is incorporated. Adjustment using this offset will ensure that bleeding *rates* are calculated and compared between treatment groups and that the variable number of days with bleeding assessments across individuals is appropriately dealt with. Subjects who obtain transfusion independence prior to Day 28 will be assumed to have zero bleeding days between the date of transfusion independence and Day 27 and treated as if they had bleeding assessed on each of those days; these days will therefore contribute to the total number of bleeding assessment days used to calculate the offset. Subjects who drop-out of the study before Day 28 for reasons other than transfusion independence will contribute bleeding data for each of the days bleeding was assessed prior to the time of drop-out; bleeding status will not be simulated beyond the time of drop-out since the use of an appropriately computed offset deals with the variable duration of follow-up.

The handling of data following the administration of an off-protocol transfusion requires discussion. Here an off-protocol transfusion is defined as the transfusion of any kind of PLT product that differs from that to which the subject was randomized (i.e. MIRASOL or CONTROL).

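### For drop-outs whose last platelet transfusion was off-protocol, the primary analysis states conflicting stopping points, and two definitions of transfusion independence decide whether zero-bleed days are added

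*SAP*

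**What the plan says.** The conflict lies within SAP Section 8.1.1. The document supplied as the protocol carries the same text, so it does not settle the matter.

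- **Drop-outs.** Subjects who leave for reasons other than transfusion independence "will contribute bleeding data for each of the days bleeding was assessed prior to the time of drop-out", and "bleeding status will not be simulated beyond the time of drop-out".
- **Off-protocol day count (N_off).** The first definition is that "the number of days bleeding was assessed during the off-protocol interval will be computed". This count sets the mean of the truncated Poisson draw and is added to the offset. The truncation limit then uses the same symbol for all off-protocol days, without the assessed condition.
- **Last transfusion off-protocol.** The rule reads: "For subjects whose last transfusion is off-protocol, bleeding will be simulated until the subject completes the transfusion period or reaches transfusion independence". Drop-out and death are not listed as stops. A note before this says that "at most 10 days of bleeding data after the last transfusion will be simulated", because a patient who goes ten days without one has become transfusion independent.
- **After transfusion independence.** If it is achieved early, "subjects will be assumed to have zero bleeds and full follow-up from the day of transfusion independence until Day 27 inclusive".

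Transfusion independence itself has two forms. Section 6.1 requires the ten transfusion-free days to fall before last contact or Day 28. Section 8.2.2, item 2 (time to first bleed) has a similar limit, using last follow-up or Day 27. Sections 7.7 and 8.1 define it only as the last of ten consecutive days without a platelet transfusion, with no last-contact condition.

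**The concern.** A subject who dies or withdraws after an off-protocol last transfusion, and before transfusion independence, falls under two rules with different end points. No text says which prevails. The rule without a drop-out stop is the later and more specific one, so a programmer could reasonably follow it.

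The choice sets both the count and the offset for these subjects in the negative binomial model that tests the 1.6 margin. It also travels. The same simulated data are reused wherever later analyses call for them, including the per-protocol and subgroup analyses, and Section 8.6 applies the primary off-protocol convention at the interim analysis.

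**Working it through.** **1. The plan's own figure.** Section 6.3.3 states about 85% power with 558 mITT subjects (279 per arm), true ratio 1.1 and one-sided 0.025; the margin of 1.6 is in Section 8.1.3. The control rate and dispersion are not given, so the 85% cannot be reproduced, only back-solved:

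SE = (ln 1.6 − ln 1.1) / (1.960 + 1.036) = 0.3747 / 2.996 = 0.125.

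For assumed control means of 1 to 4 bleeding days per 28 and dispersion of 0.5 to 3, power runs from 0.605 to 0.999. The 85% is therefore attainable but not verifiable. It does not depend on this point. SE = 0.125 is used only for scale below.

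**2. One subject under each reading.** Assumed subject: on-protocol Days 0–4 with one bleeding day, so r = 1/5 = 0.2; off-protocol last transfusion on Day 5; Day 7 the last assessed day.

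| Reading | Off-protocol days simulated | Expected simulated bleeding days | Zero-bleed days | Count / days | Rate per day |
|---|---|---|---|---|---|
| Drop-out rule with assessed-day N_off | 3 (Days 5–7) | 0.588 | 0 | 1.588 / 8 | 0.199 |
| Literal last-off-protocol rule, no transfusion independence | 10 (Days 5–14) | 2.0 | 0 | 3.0 / 15 | 0.200 |
| Literal rule plus Section 7.7/8.1 definition | 10 (Days 5–14) | 2.0 | 13 (Days 15–27) | 3.0 / 28 | 0.107 |

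The simulated column is the mean of a Poisson with mean r × N_off truncated at N_off. For N_off = 3 the mean is 0.6, and (0.6 + 0.36 + 0.108) / (1 + 0.6 + 0.18 + 0.036) = 1.068 / 1.816 = 0.588.

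The second row stops at Day 14 to isolate the effect of the simulated days. They leave the rate about unchanged and add unobserved days to the offset. The fall of 46% (1 − 0.107/0.199) comes from the zero-bleed days. In the third row 20 of the 28 days were never lived on study: 7 simulated and 13 zero-bleed.

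**3. Trial level, third reading.** Assume that every affected subject follows this pattern, bleeds at the arm's rate while at risk, and that all others have 28 assessed days. Everyone is then credited with 28 days, so the fitted arm rate is the true rate times (1 − f × 13/28), where f is the share affected. Under the drop-out rule the arm rate is unbiased. Solving the expected negative binomial score equation gave the same ratios at control means of 2, 3 and 4.

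One-sided error at the margin is 1 − Φ(1.960 − shift/0.125), where shift = ln(1.6 / estimate).

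| MIRASOL / CONTROL affected (assumed) | True 1.60 estimated as | True 1.10 estimated as | One-sided error at the margin |
|---|---|---|---|
| 2% / 0% | 1.585 | 1.090 | 3.0% |
| 5% / 0% | 1.563 | 1.074 | 3.8% |
| 10% / 0% | 1.526 | 1.049 | 5.7% |
| 10% / 2% | 1.540 | 1.059 | 4.9% |
| 10% / 10% | 1.600 | 1.100 | 2.5% |

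For 10% / 0%: 1.6 × (1 − 0.10 × 13/28) = 1.6 × 0.9536 = 1.526; shift 0.0474; 1.960 − 0.379 = 1.581; tail 5.7%.

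An excess in CONTROL acts the other way. With 0% / 5%, 1.6 / (1 − 0.05 × 13/28) = 1.6 / 0.9768 = 1.638.

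**The case against.** The strongest reply is that the plan, read as a whole, already blocks both credits. Days after drop-out are not assessed, so the first definition of N_off excludes them. A subject who leaves before the tenth transfusion-free day has not reached transfusion independence under Section 6.1 and earns no zero-bleed days. The zero-fill sentence is itself conditional on transfusion independence being achieved. Section 8.1.2 repeats for both secondary analyses that nothing is imputed after drop-out.

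Most of this stands, and it limits the point. A reader might infer from "at most 10 days of bleeding data after the last transfusion will be simulated as patients going ten (10) days without a transfusion" that every subject with an off-protocol last transfusion is deemed transfusion independent by the tenth day. It does not say that: it covers patients who actually go ten days, and the ten days are a ceiling. Nor does the last-off-protocol rule by itself halve anyone's rate; that also needs the unbounded definition.

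The reply does not remove the conflict. The safe reading requires choosing Section 6.1 over Sections 7.7 and 8.1, the assessed-day meaning of N_off over the looser one, and the general drop-out rule over the specific one. The plan directs none of these choices, Section 7.7 is where the treatment period is defined, and the statements in Section 8.1.2 govern other analyses.

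**Conclusion.** The point holds as a conflict between stated rules in the primary analysis, not as a demonstrated bias. One coherent reading credits no days after drop-out; the literal last-off-protocol rule adds simulated days with little effect on the rate; that rule together with the Section 7.7/8.1 definition adds zero-bleed days and roughly halves the example subject's rate.

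The trial-level size rests on shares that the documents do not give. At 2% to 10% in MIRASOL only, the estimate at the margin falls from 1.60 to between 1.585 and 1.526, and one-sided error rises from 2.5% to between 3.0% and 5.7%. The 10% against 0% case is at the extreme of what was assumed.

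A reader might infer that the error always favours non-inferiority. The documents do not support that. An excess in MIRASOL is plausible, because Section 7.12 treats allowed control units as compliant for MIRASOL subjects while Section 7.14 makes them off-protocol. But the frequency of drop-out after such a last transfusion is not stated for either arm. Zero-bleed days for subjects who truly reach transfusion independence before leaving are part of the design and are not in question.

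**What to change.** Make three aligned edits to the SAP:

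1. In Section 8.1.1, end simulation for subjects whose last transfusion is off-protocol at the earliest of period completion, transfusion independence, drop-out or death, and simulate assessed days only.
2. In Sections 7.7 and 8.1, apply the Section 6.1 last-contact condition to transfusion independence, and state that a subject who leaves before the tenth transfusion-free day receives no zero-filled days.
3. In Section 8.1.1, keep the assessed-day meaning of N_off throughout, including as the truncation limit.

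The interim analysis inherits the change through Section 8.6. The cost is a short text edit and one condition in the derivation, with no new data. The edits follow the drop-out rule that the SAP already states. The estimated ratio may become slightly less favourable to MIRASOL than under the literal reading.
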